Table 3: Double-blind Maintenance Phase

Visit	1 (Screening) ^a	Recommended Telephone call ^b	2 (Baseline) ^a	5	5.1	5.2	6 ^c
Day/Month^d	Day -21 to -3	Day -7 to -4	Week 0	Weeks 2-4	Week 13	Week 26/ Withdrawal	Follow-up
Review DUCS instructions, ability to read and understand e-diary with subject/caregiver	✓						
Subject/caregiver e-diary entry: rectal bleeding, stool frequency, DUCS _h and Overall Current Health ^h	✓		✓		✓	✓	
Assessment of e-diary compliance ^a		✓					
Global Change in Health ⁱ						✓	
IMPACT III ⁱ			✓			✓	
PUCAI (where applicable)			✓			✓	
Average stool frequency ^{j, k, l}			✓		✓	✓	
Average rectal bleeding ^{j, k, l}			✓		✓	✓	
PGA ^{k, l}			✓			✓	
Endoscopy (flexible sigmoidoscopy or colonoscopy) for study eligibility ^{d, l, m}	✓		✓				
Endoscopy (flexible sigmoidoscopy or colonoscopy), where possible ^j						✓	
IRT entry	✓		✓	✓	✓	✓	
Calculate partial UC-DAI			✓			✓	
Investigational product dispensed			✓	✓	✓		
Investigational product collected and compliance calculated				✓	✓	✓	
Adverse events	✓	✓	✓	✓	✓	✓	✓
Concomitant medication	✓		✓		✓	✓	✓

Table 3: Double-blind Maintenance Phase

Visit	1 (Screening) ^a	Recommended Telephone call ^b	2 (Baseline) ^a	5	5.1	5.2	6 ^c
Day/Month ^d	Day -21 to -3	Day -7 to -4	Week 0	Weeks 2-4	Week 13	Week 26/ Withdrawal	Follow-up

Abbreviations: DUCS=Daily Ulcerative Colitis Scale for children and caregivers; eCRF=electronic case report form; e-diary=electronic diary; IRT=interactive response technology; PGA=Physician's Global Assessment; PUCAI=Pediatric Ulcerative Colitis Activity Index; UC-DAI=Ulcerative Colitis Disease Activity Index.

^a The Screening Visit (Visit 1) and the Baseline Visit (Visit 2) in Table 3 apply only to subjects entering directly into the Double-blind Maintenance Phase.

^b Approximately 4 to 7 days prior to the Baseline Visit (Visit 2) and prior to each subsequent visit (Visits 5, 5.1, and 5.2), it is recommended that site staff telephone the subject or the subject's caregiver to remind them to enter UC-DAI symptoms (rectal bleeding and stool frequency) into the e-diary every night, even if the subject has no symptoms.

^c Follow-up assessment may be performed via telephone call within 7 days of the last dose of investigational product.

^d A visit window of ± 3 days is permitted for all study visits except for the Screening Visit (Visit 1) (must be 3 to 21 days) and the Baseline Visit (Visit 2), which must occur 3 to 21 days following the Screening Visit (Visit 1). If the initial endoscopy is not adequate for mucosal healing score assignment due to inadequate bowel preparation, to allow for a repeat endoscopy to be conducted, the period of the Screening Visit (Visit 1) can be extended by an additional 14 days from the date of the initial endoscopy.

^e The serum pregnancy test will be performed for all female subjects of childbearing potential at the screening visit (Visit 1) and Week 26/Withdrawal (Visit 5.2). Urine pregnancy tests will be performed at all other visits.

^f [REDACTED]
Stool samples collected for culture may be processed by local laboratories in addition to the assessment by the central laboratory. Central laboratory results will prevail and, as such, they will be the data entered into the eCRF.

^h Rectal bleeding, stool frequency, DUCS and Overall Current Health e-diary entry is completed once a day before bedtime every day during the Screening Visit (Visit 1), preferably for at least the 3 days immediately prior to the Baseline Visit (Visit 2). Rectal bleeding, stool frequency, DUCS and Overall Current Health e-diary entry is completed once a day before bedtime for the 5 days immediately prior to Visit 5.1 and Visit 5.2.

ⁱ Global Change in Health to be completed by caregivers of children aged 5-10 years and by children aged 11-17 years; IMPACT III to be completed by children aged 8-17 years only.

^j The average stool frequency and rectal bleeding scores will be calculated and available to the investigator through a report from the e-diary provider.

^k Components of the partial UC-DAI.

^l Components of the modified full UC-DAI.

^m For subjects entering the Double-blind Maintenance Phase directly: Subjects with a previously confirmed diagnosis must have endoscopy at the Screening Visit (Visit 1) or at the Baseline Visit (Visit 2). If the initial endoscopy is not adequate for mucosal healing score assignment due to inadequate bowel preparation, to allow for a repeat endoscopy to be conducted, the period of the Screening Visit (Visit 1) can be extended by an additional 14 days from the date of the initial endoscopy.

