17. Treatment with anti-diarrheals and/or anti-spasmodics within 3 days prior to the Screening Visit (Visit 1).
18. Vaccination/immunization within 21 days prior to the Screening Visit (Visit 1).
19. Predisposed to the development of myo- or pericarditis.
20. Previously been randomized into this study and withdrawn.

21. Current or recurrent disease that could affect the action, absorption, or disposition of the investigational product, or could affect clinical or laboratory assessments.
22. Current or relevant history of physical or psychiatric illness, any medical disorder that may require treatment, including surgery, or make the subject unlikely to fully complete the study, or any condition that presents undue risk from the investigational product or procedures.
23. Current use of any medication (including over-the-counter, herbal, or homeopathic preparations) that could affect (improve or worsen) the condition being studied, or could affect the action, absorption, or disposition of the investigational product(s), or clinical or laboratory assessment. (Current use is defined as use within 21 days of the Screening Visit [Visit 1], or pharmacokinetic equivalent of 5 half-lives, whichever is longer.)
24. Known or suspected intolerance or hypersensitivity to the investigational product(s) (aminosalicylates [5-ASA]), closely related compounds (including but not limited to salicylates), or any of the stated ingredients.
25. Known history of alcohol or other substance abuse within the last year.
26. Within 30 days prior to the first dose of investigational product:
 - Have used an investigational product
 - Have been enrolled in a clinical study (including vaccine studies) that, in the investigator's opinion, may impact this study.

Double-blind Acute Phase:

27. Mucosal appearance (defined by endoscopic score=0 or 1) based on central reading or local reading (if central reading is not available) at the Screening Visit (Visit 1) or Baseline Visit (Visit 2).
28. Current relapse on a 5-ASA dose higher than the low dose tested in the study (900mg for subjects weighing 18 to \leq 23kg, 1200mg for subjects weighing >23 to \leq 35kg, 1800mg for subjects weighing >35 to \leq 50kg, and 2400mg for subjects weighing >50 to \leq 90kg).
29. Acute flare with onset >6 weeks prior to the Baseline Visit (Visit 2) if being treated with 5-ASA for the flare. There is no limit to the onset of flare prior to the Baseline Visit (Visit 2) if the flare is untreated.

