The primary efficacy endpoint for the Double-blind Maintenance Phase is defined as the proportion of subjects who have maintained a clinical response (defined as partial UC-DAI ≤ 1 with rectal bleeding=0 **and** stool frequency ≤ 1 **and** PGA=0) at Week 26. This endpoint will be compared between treatment arms using a Cochran-Mantel-Haenszel (CMH) test stratifying by Week 8 responder status.

Secondary Efficacy Endpoints

Double-blind Acute Phase:

- The proportion of subjects with a clinical and endoscopic response at Week 8, defined as UC-DAI ≤ 2 with rectal bleeding=0 **and** stool frequency ≤ 1 **and** PGA=0, **and** with mucosal healing (endoscopy score ≤ 1) based on central reading. In addition, there must be at least a 1-point reduction in endoscopy score from baseline. This endpoint will be compared between treatment arms using a continuity-corrected chi-squared test.
- The proportion of subjects with a clinical and endoscopic response at Week 8, defined as UC-DAI ≤ 2 with rectal bleeding=0 **and** stool frequency ≤ 1 **and** PGA=0, **and** with mucosal healing (endoscopy score ≤ 1) based on local reading. In addition, there must be at least a 1-point reduction in endoscopy score from baseline. This endpoint will be compared between treatment arms using a continuity-corrected chi-squared test.
- The change in the DUCS score from baseline to Week 8 of the Double-blind Acute Phase. This endpoint will be compared between treatment arms using an analysis of covariance, including the baseline DUCS score as a covariate in the model.
- The percentage of subjects with an improvement (change of ≥ 20 points) in PUCAI score from baseline to Week 8 of the Double-blind Acute Phase. This endpoint will be compared between treatment arms using a continuity-corrected chi-squared test.

Double-blind Maintenance Phase:

- The proportion of subjects who have maintained a clinical and endoscopic response at Week 26, defined as UC-DAI ≤ 2 with rectal bleeding=0 **and** stool frequency ≤ 1 **and** PGA=0, **and** with mucosal healing (endoscopy score ≤ 1) based on central reading. This endpoint will be compared between treatment arms using a CMH test stratifying by Week 8 responder status.

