4.1 Inclusion Criteria

The subject will not be considered eligible for the study without meeting all of the criteria below.

General:

1. Ability to voluntarily provide written, signed, and dated (personally or via a legally authorized representative [LAR]) informed consent or assent as applicable to participate in the study.
2. Subject's parent/LAR demonstrates an understanding, ability, and willingness to fully comply with study procedures and restrictions.
3. Male and female children and adolescents aged 5-17 years, inclusive, at the Baseline Visit (Visit 2).
4. Body weight 18-90 kg at the Screening Visit (Visit 1) and the Baseline Visit (Visit 2).
5. Male, or non-pregnant, non-lactating female who agrees to comply with any applicable contraceptive requirements of the protocol or females of non-childbearing potential.
6. Diagnosed with mild to moderate UC, established by sigmoidoscopy or colonoscopy with compatible histology. Screened subjects may also have an unconfirmed diagnosis of mild to moderate UC; however, the diagnosis of mild to moderate UC must have been established by sigmoidoscopy or colonoscopy with compatible histology prior to the Baseline Visit (Visit 2).

7. Subject is able to swallow the investigational product whole.

Double-blind Acute Phase:

8. Partial UC-DAI score ≥ 2 (with a combined rectal bleeding **and** stool frequency score ≥ 1 **and** PGA=1 or 2) **and** with mucosal appearance (endoscopy score)=2 or 3 at the Baseline Visit (Visit 2), for which 5-ASA would be used as part of normal treatment.
9. If the subject is on 5-ASA treatment prior to study entry, then the dose must be stable. Stable therapy is defined as no change in dose, or no initiation of 5-ASA, from the onset of the current acute flare through discontinuation of therapy (required at the Baseline Visit; Visit 2). See exclusion criterion 28 for an additional 5-ASA dose-related requirement.

Double-blind Maintenance Phase:

10. Partial UC-DAI ≤ 1 (with rectal bleeding=0 **and** stool frequency ≤ 1 **and** PGA=0) **and** with mucosal appearance (endoscopy score)=0 or 1 at the Baseline Visit (Visit 2).

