Mucosal appearance (endoscopy score) entry criterion should be assessed based on the central reader score, if available. Only in the event that the central reader score is not available at the time of the Baseline Visit (Visit 2) should the local reading be used. However, the central reader's score will be used for the calculation of the full UC-DAI score.

Please see a description of criteria used for endoscopic scoring in [Appendix 2](#).

Stool collection (for eligibility assessments, [REDACTED] [REDACTED]) may occur at any time during the period of the Screening Visit (Visit 1), provided that written informed consent/assent has been collected before this procedure. If a standard of care stool sample has been collected within 24 hours prior to the Screening Visit (Visit 1), this sample may be used for screening assessments and evaluations provided that written informed consent/assent has been collected before the stool is sent for laboratory analysis. Stool samples collected for culture may be processed by local laboratories; however, results from the central laboratory analysis will prevail and will be entered into the eCRF.

Subjects with positive stool cultures for any enteric pathogen (see Section 4.2) will not be eligible for the study.

Results for eligibility assessments must be available and evaluated prior to the end of the period of the Screening Visit (Visit 1) and prior to randomization at the Baseline Visit (Visit 2).

Instructions relative to the use of the e-diary for UC-DAI symptoms (rectal bleeding and stool frequency), the DUCS, and Overall Current Health entry will be reviewed with the subject and/or caregiver, and a training diary entry must be completed prior to live data entry. Starting from the first evening of the period of the Screening Visit (Visit 1), each subject and/or caregiver will be instructed to complete the e-diary every night before bedtime during the period of the Screening Visit (Visit 1). It is recommended that site staff telephone the subject or the subject's caregiver approximately 4 to 7 days prior to each visit to remind them to answer the questions in the e-diary every night, even if they have no symptoms. It is of particular importance to remind the subject at least 3 days prior to the Baseline Visit (Visit 2) to complete the questions in the e-diary as this information is required to assess the eligibility of the subject.

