7.2.1.2 Modified Full UC-DAI Score

The full UC-DAI is widely used to assess treatment efficacy in subjects with mild to moderate UC (Schroeder et al. 1987; Sutherland et al. 1987). It consists of 4 individual parameters: stool frequency, rectal bleeding, endoscopy score (mucosal appearance), and PGA. For the purpose of this study, the standard UC-DAI scale has been modified so that an endoscopy score of mild disease does not include friability; instead, friability will be scored as 2: moderate disease.

Please see a description of stool frequency, rectal bleeding and PGA in Section [7.2.1.1](#).

All 4 parameters will be assessed individually on a scale from 0-3; the maximum total modified full UC-DAI score is 12.0. The modified full UC-DAI score will be calculated at Baseline (Visit 2), Week 8 of the Double-blind Acute Phase (Withdrawal) for subjects not entering into the Open-label Acute Phase, Week 8 of the Open-label Acute Phase (Withdrawal) for subjects who have not had endoscopy at the end of the Double-blind Acute Phase, and Week 26 of the Double-blind Maintenance Phase (Withdrawal) visits. The total score will be calculated by summing the individual scores for the 4 parameters (endoscopy score will be based on the central reader's score). The site is not required to calculate the full UC-DAI; this will be calculated centrally using e-diary and eCRF data.

For determination of the modified full UC-DAI, the average of the symptom scores of the last available 3 days within the 5-day period immediately prior to study visits where endoscopic data are available, will be used. No symptom data older than 5 days prior to the study visit will be used. Data collected on days when bowel preparations have been administered or when endoscopy has been performed will be excluded.

An endoscopy must be performed and mucosal appearance scored within 21 days prior to the Screening Visit (Visit 1), during the Screening period or at the Baseline Visit (Visit 2) depending on the subject's UC history and phase of the study into which they are entering. All efforts should be made to perform endoscopy at Week 8 of the Double-blind Acute Phase (or Week 8 of the Open-label Acute Phase, as applicable), Week 26 of the Double-blind Maintenance Phase, or the subject's withdrawal if different from these visits.

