5.8.2.1 Double-blind Acute Phase

- The proportion of subjects with a clinical and endoscopic response at Week 8, defined as UC-DAI ≤ 2 with rectal bleeding=0 and stool frequency ≤ 1 and PGA=0, and with mucosal healing (endoscopy score ≤ 1) based on central reading. In addition, there must be at least a 1-point reduction in endoscopy score from baseline. This endpoint will be compared between treatment arms using a continuity corrected chi-squared test. If any of the expected cell counts are very low (i.e., less than 5), then Fisher's Exact Test will be used as an alternative analysis method. Subjects with missing data at Week 8 will be assumed not to have had a clinical response. Subjects who completed week 8 but who did not have central reading endoscopies at both baseline and week 8 will be excluded.
- The proportion of subjects with a clinical and endoscopic response at Week 8, defined as UC-DAI ≤ 2 with rectal bleeding=0 and stool frequency ≤ 1 and PGA=0, and with mucosal healing (endoscopy score ≤ 1) based on local reading. In addition, there must be at least a 1-point reduction in endoscopy score from baseline. This endpoint will be compared between treatment arms using a continuity corrected chi-squared test. If any of the expected cell counts are very low (i.e., less than 5), then Fisher's Exact Test will be used as an alternative analysis method. Subjects with missing data at Week 8 will be assumed to be treatment failures. Subjects with missing data at Week 8 will be assumed not to have had a clinical response. Subjects who completed week 8 but who did not have local reading endoscopies at both baseline and week 8 will be excluded.
- The change in the DUCS score from baseline to Week 8 of the Double-blind Acute Phase. This endpoint will be compared between treatment arms using an analysis of covariance (ANCOVA), including treatment arm as a factor and the baseline DUCS score as a covariate in the model.
- The percentage of subjects with an improvement (change of ≥ 20 points) in PUCAI score from baseline to Week 8 of the Double-blind Acute Phase. This endpoint will be compared between treatment arms using a continuity corrected chi-squared test. If any of the expected cell counts are very low (i.e., less than 5), then Fisher's Exact Test will be used as an alternative analysis method. Subjects with missing data at Week 8 will be assumed not to have had a clinical response.

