8.2 Derived Efficacy Endpoints

- Stool frequency and rectal bleeding score:
 - For both stool frequency and rectal bleeding, the symptom score (collected via the electronic diary [e-diary]) is defined as the average of the scores from the last available 3 days from the 5 days immediately prior to the visit (days -1 to -5). If there are fewer than 3 days of data available during days -1 to -5, the average will be calculated from any available days within the period. If there are no available days during the period, then the symptom score will be missing for that visit. Data collected on days when bowel preparations have been administered or when endoscopy has been performed will be excluded.
 - For stool frequency and rectal bleeding, the symptom score will be grouped into a category (0, >0 - <1, 1 - <2, 2 - <3, and 3).
- Partial UC-DAI score:
 - Sum of rectal bleeding score, stool frequency score and PGA score
- Full UC-DAI score:
 - Sum of rectal bleeding score, stool frequency score, PGA score and endoscopy score
- Clinical response: partial UC-DAI ≤ 1 (rectal bleeding=0 and stool frequency ≤ 1 and PGA=0)
- Clinical and endoscopic response: UC-DAI ≤ 2 with rectal bleeding=0 and stool frequency ≤ 1 and PGA=0, and mucosal healing (endoscopy score ≤ 1) based on central reading
- Week 8 responder status is defined based on clinical response: entered Maintenance Phase directly, responder at Week 8 of the Double-blind Acute Phase, or responder at Week 8 of the Open-label Acute Phase.

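### The acute clinical-and-endoscopic response requires a 1-point fall from the same reader's baseline, but entry needs a 2 or 3 from one reader only, so a child scored 0 at baseline by the analysed reader is counted but cannot respond

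*Protocol*

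**What the plan says.** **Endpoint.** The Protocol Synopsis, Protocol 9.8.3.1 and SAP 5.8.2.1 define two versions of the acute-phase clinical-and-endoscopic response at Week 8, one on central and one on local reading. Each needs the symptom and PGA criteria, a full UC-DAI of 2 or less, an endoscopy score of 1 or less, and one further condition: "In addition, there must be at least a 1-point reduction in endoscopy score from baseline". The score is bounded: "All 4 parameters will be assessed individually on a scale from 0-3" (Protocol 7.2.1.2).

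**Whose baseline.** The clause does not name the reader. SAP 5.8.2.1 settles it by implication. For the central version: "Subjects who completed week 8 but who did not have central reading endoscopies at both baseline and week 8 will be excluded". For the local version: "Subjects who completed week 8 but who did not have local reading endoscopies at both baseline and week 8 will be excluded". These exclusions concern missing readings only; nothing is said about a low baseline.

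**Entry.** Protocol 4.1, criterion 8, asks for a child "with mucosal appearance (endoscopy score)=2 or 3 at the Baseline Visit (Visit 2") and does not name the reader. Exclusion criterion 27 removes children scored 0 or 1, "based on central reading or local reading (if central reading is not available"). Protocol 7.1.1.1 makes the central score the default and says that only when the "central reader score is not available at the time of the Baseline Visit (Visit 2) should the local reading be used". No section requires both readers to score 2 or more.

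**General definition.** The Definitions page of the Protocol and the entry in SAP 8.2 beginning "Clinical and endoscopic response: UC-DAI" give the response without the 1-point fall.

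**The concern.** Entry and analysis can rest on different readers. One reader's 2 or 3 admits the child, and the other reader's baseline, possibly 0 or 1, can then be the starting point for a required fall. Such a child has both readings, so the missing-reading exclusion does not apply and the child remains in the denominator.

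What is at stake is the response rate per dose on two named secondary endpoints. The trial is described as an estimation study with descriptive p-values, so these rates are themselves the result. A child who fails because of the scoring rule says nothing about either dose, yet lowers the estimate for the arm the child is in.

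**Working it through.** The plan gives no figure for this endpoint to reproduce. The check has three parts.

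**1. Which scores can count.** The rule is: Week 8 score ≤1, and baseline minus Week 8 ≥1, both from the same reader, on a 0–3 scale.

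| Same-reader baseline | Week 8 scores that count with the clause | Without the clause |
|---|---|---|
| 0 | none | 0 or 1 |
| 1 | 0 only | 0 or 1 |
| 2 | 0 or 1 | 0 or 1 |
| 3 | 0 or 1 | 0 or 1 |

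From 2 or 3, reaching ≤1 already gives a fall of at least 1, so the clause is redundant. It acts only on children whose analysed reader scored 0 or 1 at baseline.

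**2. How such a child gets in.**
- Local-reading endpoint: entry on a central 2 or 3, which is the default route, with a local baseline of 0 or 1.
- Central-reading endpoint: entry on a local 2 or 3 because the central score was not available at Visit 2, with the central baseline then read as 0 or 1. If it is never read, a Week 8 completer is excluded rather than counted as a failure.

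A baseline of 0 needs the readers to differ by at least 2 points. A baseline of 1 needs a difference of only 1 point when the entry score is 2.

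**3. Size, under assumptions.** Let p be the response rate among children with a same-reader baseline of 2 or 3, d the share of the denominator with a same-reader baseline of 0 or 1, and s the share of those who are at 1. Assume that a child at 1 has half the usual chance, p/2, of meeting the target of 0. None of these values is in the documents.

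Reported rate = (1 − d)p + d·s·p/2 + d·(1 − s)·0

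Loss = p − reported rate = d·p·(1 − s/2)

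The loss therefore runs from 0.5·d·p (all at baseline 1) to d·p (all at baseline 0).

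| d | Loss at p = 50% | Loss at p = 30% |
|---|---|---|
| 10% | 2.5 to 5.0 points | 1.5 to 3.0 points |
| 20% | 5.0 to 10.0 points | 3.0 to 6.0 points |
| 30% | 7.5 to 15.0 points | 4.5 to 9.0 points |

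With the same d and s in both arms, a dose difference is multiplied by 1 − d(1 − s/2). At d = 10% an assumed 20-point difference becomes 20 × 0.90 = 18 to 20 × 0.95 = 19 points.

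**A related point on the total score.** On one reader's score, UC-DAI ≤2 follows from the other criteria: bleeding 0 + stool frequency ≤1 + PGA 0 + endoscopy ≤1 is at most 2. But Protocol 7.2.1.2 and SAP 4.2.1 build the full UC-DAI on the central score. If that total were used in the local endpoint, a child with local Week 8 score 1, central score 2 and stool frequency 0.3 would total 2.3 and fail, although the local reading meets the healing criterion.

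**The case against.** **The clause has a purpose.** It stops mucosa already scored as healed from being credited as an endoscopic response. That aim is sound, and whether such a child is a failure or not evaluable is a choice of estimand. But the plan does not state that it made this choice, and treating the child as not evaluable keeps the same safeguard.

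**The two endpoints are not equally exposed.** A reader might infer that they are. The documents do not support this. Central reading decides entry by default, so the central endpoint normally uses the reader that admitted the child. Protocol 4.3 also lists late or missing endoscopy results as a reason for failed randomization, which suggests that central results are usually awaited. The central route nevertheless exists, because Protocol 7.1.1.1 provides for the local fallback and Table 1 allows the eligibility endoscopy at Visit 2.

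**SAP 8.2 need not contradict SAP 5.8.2.1.** A reader might infer a contradiction, since a child going from 1 to 1 meets the endoscopic criterion under 8.2 and fails it under 5.8.2.1. But the Definitions page and SAP 8.2 serve both phases, and the fall is not part of the Week 26 endpoints in SAP 5.8.2.2, whose direct entrants must start at 0 or 1. The acute sections add the clause expressly. What is missing is a cross-reference.

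**A gap between central and local results is not simply an artefact of the rule.** A child scored 2 by one reader and 0 by the other is reader disagreement.

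**Some of this will be visible anyway.** SAP 5.8.3.1 plans endoscopy summaries and shift tables by arm on each reading. That stands, but those tables do not change the endpoint's denominator.

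**Conclusion.** The rule creates certain non-responders at a same-reader baseline of 0 and sets a stricter target at 1. This follows from the documents, given that SAP 5.8.2.1 ties each version to its own reader's baseline. It matters mainly for the local-reading endpoint, and for the central-reading endpoint only after a late central read.

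The expected effect is lower rates in both arms and attenuation of the difference. A reader might infer bias toward one dose. Randomization gives no reason to expect that, although chance imbalance between small arms is possible.

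The size cannot be derived from the documents. The illustrative loss of 2.5 to 5 points rests on an assumed d of 10%, p of 50% and a halved chance from baseline 1. A reader might also infer that each such child costs an arm 12.6 points, from 53/2 × 0.30 = 7.95 scoped children per arm and 1/7.95. The documents do not support that figure. SAP 5.8.2.1 keeps children with missing Week 8 data in the denominator as non-responders; for example, with 8 scoped and an assumed 3, 5 or 8 withdrawals, one child is worth 9.1, 7.7 or 6.3 points. In addition, the 30% target in Protocol 7.2.1.2 combines the Double-blind and Open-label Acute Phases, so it does not give the number scoped at double-blind Week 8.

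The change is worth making because it is cheap and removes an avoidable distortion from two estimates, but these are secondary endpoints and the effect may be small.

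**What to change.** In SAP 5.8.2.1, before unblinding:

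- For each reading, analyse the children whose baseline score on that same reading is 2 or 3, applying the condition to Week 8 completers and withdrawals alike.
- Footnote Tables 14.2.2.1.1 and 14.2.2.1.2 with the number per arm not evaluable because that baseline was 0 or 1.
- Add a sensitivity analysis that counts those children as failures.
- State that UC-DAI ≤2 in the local endpoint is computed on the local score.
- In SAP 8.2, add a cross-reference to the acute-phase 1-point clause.

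The restriction rests on images taken before the first dose, so it does not disturb the randomized comparison, and it extends an exclusion the SAP already makes for missing readings. Within the analysed children the 1-point clause is met automatically by anyone who reaches ≤1. The cost is SAP wording, two footnotes, one extra analysis per reading and a slightly smaller denominator for each reading. Eligibility rules do not change.
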